8.6.3 Progression-Free Survival

The non-parametric Kaplan-Meier method will be used to estimate the PFS curve. Additional details, including censoring rules for those subjects without PD, are summarized in [Table 18](#).

Table 18 Censoring Rules for PFS

Situation	Analysis
No PD and no death; new anticancer treatment is not initiated	Censored at last disease assessment
No PD and no death; new anticancer treatment is initiated	Censored at last disease assessment before new anticancer treatment
PD or death documented after ≤ 1 missed disease assessment	Progressed at date of documented PD or death
PD or death documented after ≥ 2 missed disease assessments	Progressed at date of documented PD or death
No PD and no death and lost to follow-up after ≥ 2 missed disease assessments	Censored at last disease assessment

Abbreviation: PD = progressive disease.

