1.0 TRIAL SUMMARY

Abbreviated Title	Phase Ib trial of pembrolizumab (MK-3475) in combination with dinaciclib (MK-7965) in subjects with hematologic malignancies (KEYNOTE-155)
Trial Phase	Phase Ib
Clinical Indication	
Treatment of subjects with relapsed or refractory chronic lymphocytic leukemia, multiple myeloma (rrMM), or diffuse large B-cell lymphoma (rrDLBCL).
 
Note: The rrMM cohort was closed to enrollment on 07-AUG-2017 due to lack of efficacy, and all subjects with rrMM were discontinued from treatment. Remaining subjects with rrMM are in survival follow-up.
 
Note: The rrCLL cohort was closed to enrollment on 30-APR-2019 due to lack of accrual, and all subjects with rrCLL have discontinued from treatment. Remaining subjects with rrCLL are in survival follow-up.

Trial Type	Interventional
Type of control	No treatment control
Route of administration	Intravenous (IV)
Trial Blinding	Unblinded Open-label
Treatment Groups	Combination of pembrolizumab and dinaciclib
Number of trial subjects	Approximately 102 to a maximum of 138 subjects will be enrolled.
Estimated duration of trial	The sponsor estimates that the trial will require approximately 36 months from the time the first subject signs the informed consent until the last subject's last study-related phone call or visit.
Duration of Participation	Each subject will participate in the trial for up to approximately 26 months. Trial participation is defined as the period from the time the subject signs the Informed Consent Form through the final contact. After a screening phase of 28 days, each subject will receive combination treatment for a maximum of 35 cycles (approximately 2 years) or until documented disease progression by investigator assessment, unacceptable adverse event(s), intercurrent illness that prevents further administration of treatment, subject withdraws consent, pregnancy of the subject, noncompliance with trial treatment or procedure requirements, or administrative reasons. After the end of treatment each subject will be followed for 30 days for a Safety Follow-Up Visit. Subjects who discontinue for reasons other than disease progression will have post-treatment follow-up for disease status until disease progression, initiating a non-trial cancer treatment, withdrawing consent, or becoming lost to follow-up. All subjects will be followed by telephone for overall survival until death, withdrawal of consent, or the end of the trial.

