7.1.1.5.4 Subsequent Antineoplastic Therapy

The investigator or qualified designee will review all new antineoplastic therapy initiated after the last dose of trial treatment.

Collect transplant parameters after trial treatment to include the conditioning regimen, date, and type of transplant.

If a subject initiates a new antineoplastic therapy within 30 days after the last dose of trial treatment, the 30-day Safety Follow-up visit must occur before the first dose of the new therapy. Once new antineoplastic therapy has been initiated, the subject will move into survival follow-up.

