7.1.5.4.2 Survival Follow-up

Once a subject experiences confirmed disease progression or starts a new antineoplastic therapy, the subject moves into the survival follow-up phase and should be contacted by telephone every 12 weeks (\pm 14 days) to assess for survival status until death, withdrawal of consent, or the end of the trial, whichever occurs first. The first survival follow-up assessment should be scheduled as described below:

For participants who discontinue treatment intervention and who will not enter the efficacy follow-up phase, the first survival follow-up assessment will be scheduled 12 weeks after the discontinuation visit and/or safety follow-up visit (whichever is last).

For participants who completed assessments in the efficacy follow-up phase, the first survival follow-up assessment will be scheduled 12 weeks after the last efficacy assessment follow-up visit has been performed.

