7.1.5.4.3 Survival Status

To ensure current and complete survival data are available at the time of database locks, updated survival status may be requested during the course of the trial by the Sponsor. For example, updated survival status may be requested prior to but not limited to an external Data Monitoring Committee review, interim and/or final analysis. Upon Sponsor notification, all participants who do not/will not have a scheduled trial visit or trial contact during the Sponsor-defined time period will be contacted for their survival status (excluding participants that have a previously recorded death event in the collection tool).

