8.4 Analysis Endpoints

8.4.1 Efficacy Endpoints

Efficacy endpoints will be based on investigator assessment using the disease-specific criteria outlined in Section 7.1.2.8.

Primary

Objective Response Rate

ORR is defined as the proportion of subjects in the analysis population who achieved at least a partial response according to the disease-specific criteria (CR+PR for CLL and DLBCL; sCR+CR+VGPR (very good partial remission)+PR for MM).

Secondary

Duration of Response

For subjects who demonstrated a response (PR or better), DOR is defined as the time from first documented evidence of response until first documented evidence of disease progression or death due to any cause, whichever occurs first.

Progression-Free Survival

PFS is defined as the time from first dose of trial treatment to the first documented evidence of disease progression or death due to any cause, whichever occurs first.

Overall Survival

OS is defined as the time from first dose of trial treatment to death due to any cause.

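### Table 18 lets a later PD or death decide whether a subject who starts new anticancer therapy is censored, so Kaplan-Meier PFS at a fixed time can drift upward with the cut-off date

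*Combined protocol and SAP*

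**What the plan says.** Section 8.4.1 defines PFS as "time from first dose of trial treatment to the first documented evidence of disease progression or death due to any cause", with no stop at new therapy. Section 8.6.3 estimates it by Kaplan-Meier under Table 18, which has five rows:

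- Row 1: no event and no new treatment. Censored at the last disease assessment.
- Row 2: "No PD and no death; new anticancer treatment is initiated". The action is "Censored at last disease assessment before new anticancer treatment".
- Rows 3 and 4: PD or death after at most one, or at least two, missed assessments. The action in both is "Progressed at date of documented PD or death".
- Row 5: no event and lost to follow-up after at least two missed assessments. Censored at the last disease assessment.

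Deaths continue to be collected after a switch. Section 7.1.1.5.4 says "Once new antineoplastic therapy has been initiated, the subject will move into survival follow-up". Section 7.1.5.4.2 says that a subject who "starts a new antineoplastic therapy, the subject moves into the survival follow-up phase and should be contacted by telephone every 12 weeks". The Trial Summary adds "All subjects will be followed by telephone for overall survival until death, withdrawal of consent, or the end of the trial", and under 7.1.5.4.3 "updated survival status may be requested during the course of the trial by the Sponsor", with database locks as the stated purpose.

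Disease follow-up is described in two ways. Sections 5.5.2, 6.0 (footnote f), 7.1.1.5.4 and 7.1.5.4 end it at new therapy. Section 2.1 follows subjects who leave treatment for a transplant or other therapy until PD or the end of the trial.

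**The concern.** Take a subject with a last scan at month 4, new therapy at month 5 and death at month 14. At a month-12 cut-off, row 2 removes this subject from the risk set at month 4. At a month-15 cut-off, an event row keeps the same subject at risk through the whole first year. Nothing about the first 12 months has changed; only a later death has been learned.

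Kaplan-Meier needs the decision to censor at a given time to use only what is known by then. Here membership of the risk set at month 6 or 12 depends on what happens afterwards. A reported PFS rate or median would then partly reflect the date of the database lock, and two locks of the same cohort could differ for that reason alone.

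**Working it through.** The plan states no PFS rate, median or event count, so there is no figure of its own to reproduce. The check applies the rows of Table 18 as printed. Only the cohort size (30, Section 8.8) and the 9-week scan interval (Section 7.1.2.8, CLL and DLBCL) come from the documents. Every other input is assumed.

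**Fixed example, n = 30.** Of 24 subjects who never switch, 12 have PD before month 4, 9 between months 4 and 12, and 3 after month 12. Six subjects switch at month 5 with a last scan at month 4, and die at months 8, 11, 13, 15, 20 and 26. All 30 are followed at least 12 months.

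1. Up to month 4 there are 12 events among 30, so the first factor is 18/30.
2. After month 4 the risk set holds the 12 remaining non-switchers, the 2 switchers who die before month 12, and the k switchers whose deaths after month 12 are recorded by the cut-off. Switchers still alive are back-dated out at month 4.
3. By month 12 this group has 9 + 2 = 11 events, so S(12) = (18/30) × (3 + k)/(14 + k).

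| Cut-off (months) | k | Table 18 | Always censor at last scan before switch | Count all events |
|---|---|---|---|---|
| 12 | 0 | 18/30 × 3/14 = 12.9% | 18/30 × 3/12 = 15.0% | 7/30 = 23.3% |
| 18 | 2 | 18/30 × 5/16 = 18.8% | 15.0% | 23.3% |
| 24 | 3 | 18/30 × 6/17 = 21.2% | 15.0% | 23.3% |
| 30 | 4 | 18/30 × 7/18 = 23.3% | 15.0% | 23.3% |

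Both consistent rules give the same answer at every cut-off; Table 18 does not.

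**Direction.** Once all subjects have passed time t, each newly recorded post-switch death after t adds one subject to later risk sets before t and no event there. A factor (r − d)/r becomes (r + 1 − d)/(r + 1), which is never smaller. S(t) can therefore only stay level or rise.

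**Simulated size.** The grid had 36 scenarios: exponential median PFS of 4, 6 or 9 months; 10% or 20% switching before PD; median survival after the switch of 6, 9 or 16 months; follow-up uniform on 10–30 or 31–50 months; no PD documented after the switch. Table 18 fell short of the all-events count at 12 months by about:

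- 10–30 months of follow-up: 0.6–3.4 points at 10% switching and 1.3–6.9 at 20%.
- 31–50 months: 0.1–1.3 and 0.1–2.6 points.

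The standard error, sqrt(p(1 − p)/30), was 6.3–9.0 points at 12 months, and every shortfall was below it.

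One scenario in detail (median 4 months, 20% switching, 9 months' survival afterwards): Table 18 gives 13.1% with 10–30 months of follow-up, 15.6% with 24–36 and 16.6% with 31–50. Always censoring gives 11.4% and counting all events 17.4% in each window. If PD after the switch is documented, as Section 2.1 reads, the shift of 16.6 − 13.1 = 3.5 points falls to 0.4–1.0.

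Larger movement needs harsher inputs. In a separate set of 18 scenarios, with 10–30% switching and every subject cut at 12.5 and then at 36 months, Table 18 moved up by 1.4 to 12.3 points. The consistent rules did not move.

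**The case against.** **Intent.** Table 18 never names PD or death after new therapy. Row 2 could be read as no event at the time the new therapy starts, with rows 3 and 4 dealing only with missed assessments. That would be ordinary censoring at new therapy, and it would fit the sections that end disease follow-up there. The sponsor may have meant this. But no text says so, the event rows are unconditional, and 8.4.1 counts death from any cause without a stop. A programmer following the table would code the look-ahead. If ordinary censoring was meant, the remedy merely writes it down.

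**Yardstick.** A reader might infer that Table 18 is wrong because it lies below the 8.4.1 count, and that uniform censoring repairs this. That does not follow. In the detailed scenario uniform censoring gives 11.4% against an all-events 17.4%, while Table 18 gives 13.1–16.6%. Across the 36 scenarios Table 18 was the closer of the two in most: 22 to 26, depending on how switch and scan times are coded, and nearly all of those with long follow-up. The objection stands. The defect is the inconsistency, and choosing between the two consistent rules is a choice of estimand.

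**Completeness.** Rows 1 and 5 against row 4 contain a similar look-ahead. A subject whose scans stop without new therapy is censored at the last scan while event-free, but becomes an event with full time at risk if a death is recorded later. This also stands; a new-therapy rule does not remove it.

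**Size.** All magnitudes are assumed, and PFS is descriptive. Both points are right and limit the weight of the finding.

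**Conclusion.** The point holds as an internal inconsistency. As written, Table 18 makes censoring at new therapy depend on later outcome, and Kaplan-Meier PFS at a fixed time can drift upward with the cut-off date after all subjects have passed that time. The direction follows from the rows themselves.

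The size does not. The documents give neither the share of subjects who switch before PD nor their later survival. With no such switching the effect is zero, and in the 36-scenario grid it was below one standard error at n = 30. The fixed example and the harsher runs show the mechanism; they do not predict this trial.

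A reader might infer that the efficacy conclusions are unsound. The documents do not support that. PFS is a secondary endpoint, Section 8.3 tests no hypotheses, and ORR, the futility rule and the sample size do not use Table 18. A change is worth making because a stated rule is wrong as written and cheap to correct.

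**What to change.** 1. In Table 18, apply one new-therapy rule whatever happens later. Because most sections end disease follow-up at new therapy, the workable main rule is to limit rows 3 and 4 to PD or death before new anticancer therapy, and to censor every subject who switches before PD at the last assessment before the switch.
2. Make 8.4.1 and 8.6.2 match. In 8.6.2, also say that death without earlier PD or new therapy is a DOR event; 8.4.1 already counts death, but the censoring text omits it.
3. Report beside it PFS counting every documented PD and death regardless of new therapy, with event-free subjects kept at risk to last contact.
4. State that these are different estimands. The first assumes switching is unrelated to prognosis and can lie further from the current 8.4.1 count than Table 18 does. The second treats unobserved PD after the switch as absent.
5. State that rows 1 and 5 against row 4 keep a similar look-ahead for subjects whose scans stop without new therapy.
6. Reconcile Section 2.1 with Sections 5.5.2, 6.0 (footnote f), 7.1.1.5.4, 7.1.5.4 and 7.1.5.4.2 on disease follow-up after new therapy.

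Items 1 to 5 cost SAP wording and one extra run, with no new data; Section 8.0 allows a supplemental SAP before final database lock. Item 6 is a protocol clarification. The statistical price is that later deaths leave the main analysis. On the assumed inputs its 12-month value then sits between roughly 8–9 points below and 1–2 above the all-events count. When switching was linked to prognosis (12-month PFS without new therapy 17.5%), uniform censoring gave 12.8% if good-prognosis subjects switched sooner and 18.4% if poor-prognosis subjects did. Both results therefore need to be shown.

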8.6.4 Overall Survival

The median OS, if reached, will be estimated in the given analysis population. In addition, the Kaplan-Meier method will be used to estimate the survival curve.

Table 19 Analysis Methods for Efficacy Endpoints (Signal Detection)

Endpoint/Variable	Statistical Method	Analysis Population	Missing Data Approach
Primary:			
ORR – by investigator assessment using disease-specific criteria ^a	2-sided 95% exact confidence interval	ASaT	Subjects with missing data are considered non-responders.
Secondary:			
DOR – by investigator assessment using disease-specific criteria ^a	Summary statistics using Kaplan-Meier method	All responders	Non-responders are excluded in analysis.
PFS – by investigator assessment using disease-specific criteria ^a	Summary statistics using Kaplan-Meier method	ASaT	Censored at last assessment (see Table 18 for additional details)
OS	Summary statistics using Kaplan-Meier method	ASaT	Censored at last assessment
^a CLL based on iwCLL guidelines [1]; MM based on IMWG criteria [2]; DLBCL based on the Revised Response Criteria for Malignant Lymphoma [3]. Abbreviations: ASaT = all subjects as treated; DOR = duration of response; ORR = objective response rate; OS = overall survival; PFS = progression-free survival.			

8.6.5 Statistical Methods for Safety Analyses

In both Dose Evaluation and Signal Detection, safety and tolerability will be assessed by clinical review of all relevant parameters, including AEs, ECIs, laboratory tests, and vital signs. Summary statistics (counts, percentage, mean, standard deviation, etc.) will be provided for the safety endpoints as appropriate.

See Section 8.8 for statistical details on the dose evaluation of pembrolizumab plus dinaciclib conducted in Dose Evaluation.

8.6.6 Other Analyses

Baseline characteristics will be assessed by the use of tables and/or graphs. No statistical hypothesis tests will be performed on these characteristics. The number and percentage of subjects screened, allocated, the primary reasons for screening failure, and the primary reason for discontinuation will be displayed. Demographic variables (eg, age, gender), baseline characteristics, primary and secondary diagnoses, and prior and concomitant therapies will be summarized by descriptive statistics or categorical tables.

Additional exploratory analyses will be described in the supplemental statistical analysis plan.

8.7 Interim Analysis

In Signal Detection, a futility analysis will be conducted separately within each cohort. After the first 12 subjects are evaluable for efficacy (treated and with at least one post-baseline

disease assessment), the ORR will be evaluated according to the disease-specific criteria. Enrollment would not be paused within a cohort during the futility evaluation. For the MM and DLBCL cohorts, if 0 responses are observed among the 12 subjects, which would rule out an ORR of 17% with 90% confidence (1-sided), the cohort may be terminated; for the CLL cohort, if 2 or fewer responses are observed among the 12 subjects, which would rule out an ORR of 39% with 90% confidence (1-sided), the totality of the data including both safety and efficacy will be evaluated to decide whether or not to continue enrollment in that cohort.

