In the Signal Detection phase, approximately 30 subjects each with rrCLL, rrMM, or rrDLBCL will be enrolled in separate cohorts. The Dose Evaluation and Signal Detection phases will further evaluate safety and characterize preliminary efficacy.

In the Signal Detection phase, an interim analysis for safety and an efficacy interim analysis for futility will be conducted for each cohort after 12 subjects have been enrolled and the last subject has completed the first response assessment (ie, after Cycle 3 for CLL and rrDLBCL, and after Cycle 2 for rrMM), or otherwise discontinued trial treatment. Enrollment will be paused during the interim analysis (Section 8.7). The results will be reviewed by the trial

[figure not shown]
team. Enrollment may resume in that cohort if the results of the safety and efficacy analysis justify continuing.

Subjects will continue on treatment until disease progression (PD) (Section 7.1.2.7 and Section 7.1.2.8), unacceptable adverse event (AE), or treatment has been completed (ie, 35 cycles [approximately 2 years]). Subjects who discontinue treatment before PD, including subjects who discontinue treatment for bone marrow transplantation or to receive any other treatment, will be followed every 12 weeks for at least 12 months until PD is documented or until the end of the trial.

The primary objective of the trial is to evaluate the safety and tolerability of the combination of pembrolizumab and dinaciclib in subjects with hematologic malignancies. Secondary objectives by tumor type include the ORR, duration of response (DOR), progression-free survival (PFS), and overall survival (OS).

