12.7 Revised iwCLL Response Guidelines

CLL response assessment is based on the 2008 International Workshop (iwCLL) guidelines (Blood 2008;111:5446-5456) with the following clarifications/revisions.

NCI-WG CLL Response Criteria^A	
Complete Remission (CR)	
Requires ALL of the following criteria as assessed at least 2 months after completion of therapy:	
Peripheral blood lymphocytes (x10 ⁹ /L)	<4
Lymphadenopathy	None by physical exam and CT scan
Hepatomegaly or splenomegaly	None by physical exam and CT scan
Symptoms	None
Blood counts:	
Neutrophils (x10 ⁹ /L), and	>1.5 without need for exogenous growth factors
Platelets (x10 ⁹ /L), and	>100 without need for exogenous growth factors
Hemoglobin (g/dL)	>11 without red blood cell transfusion or need for exogenous erythropoietin
Bone marrow	For subjects in clinical trials, at least 2 months after the last treatment and if clinical and laboratory criteria for CR has been achieved: normal cellularity for age; <30% of nucleated cells are lymphocytes; no lymphoid nodules. If hypocellular, repeat bone marrow biopsy at 4 weeks, or until peripheral blood counts have recovered (time interval should not exceed 6 months after last treatment).
CR with Incomplete Marrow Recovery (CRi)	
Meets all criteria for CR but have persistent anemia or thrombocytopenia or neutropenia related to drug toxicity	
Nodular Partial Remission	
Meets all criteria for CR but lymphoid nodules are present in the bone marrow sample obtained at least 2 months after last treatment.	
Partial Remission (PR)	
The following criteria must be documented for a minimum of 2 months:	

Blood lymphocytes, and
 
Lymphadenopathy, and
	
≥50% decrease from baseline
 
≥50% decrease in the sum products of up to 6 lymph nodes or in the largest diameter of the enlarged lymph node(s) from baseline.
 
and
 
No increase in any lymph node, and no new enlarged lymph node (in lymph nodes <2 cm, an increase of < 25% is not considered significant)

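### Does the CLL futility statement at 2 of 12 need changing because a partial remission takes 2 months to document?

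*Combined protocol and SAP*

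**What the plan says.** Section 8.7 evaluates futility in each Signal Detection cohort once 12 subjects have been treated and have at least one post-baseline disease assessment. For CLL it states: "if 2 or fewer responses are observed among the 12 subjects, which would rule out an ORR of 39% with 90% confidence", one-sided. The stated consequence is a review of all safety and efficacy data before deciding whether enrollment continues. The summary in Section 8.1 says a cohort may terminate.

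Section 2.1 times the look at the point when "the last subject has completed the first response assessment", which for CLL is after Cycle 3, or when that subject has discontinued treatment.

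Response is scored by the disease-specific criteria. Section 8.4.1 reads: "ORR is defined as the proportion of subjects in the analysis population who achieved at least a partial response according to the disease-specific criteria". For CLL those criteria are in Section 12.7. For partial remission: "The following criteria must be documented for a minimum of 2 months". For complete remission: "Requires ALL of the following criteria as assessed at least 2 months after completion of therapy".

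Section 7.1.2.8.1 spaces CLL scans about 9 weeks apart. Section 8.7 does not say whether a partial remission seen once, and not yet documented for 2 months, counts at the look.

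**The concern.** Read literally, these sections do not fit together. The first CLL scan falls at about week 9 and the second at about week 18. A subject on treatment with only the first scan cannot have 2 months of documented partial remission, however good that scan is. The complete-remission wording is out of reach for anyone still on therapy. At least the last of the 12 may therefore be counted as a non-responder simply because the look came early.

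An upper confidence limit on ORR from 2 of 12 treats the other 10 as true non-responders. If some are only pending, a count of 2 excludes less than the plan says. The combination could then look worse than it is, and the cohort could be stopped partly on a confidence level that the look did not deliver.

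**Working it through.** **Inputs.** From Section 8.7: 12 subjects, boundary of 2 or fewer responses, excluded ORR 39%, one-sided 90% confidence. From Section 7.1.2.8.1: scans every 9 weeks (63 days). Accrual is not given in the documents, so the number of unsettled subjects, k, is an assumption. A subject is settled once he or she has responded, progressed or discontinued.

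**Step 1: the plan's figure.** With X distributed Bin(12, 0.39):

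P(X ≤ 2) = 0.61^12 + 12 × 0.39 × 0.61^11 + 66 × 0.39² × 0.61^10 = 0.0027 + 0.0204 + 0.0716 = 0.0946.

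Confidence is 1 − 0.0946 = 90.5%. The exact (Clopper-Pearson) one-sided 90% upper limit is the 0.90 quantile of Beta(3, 10), which is 38.55%. The stated 39% is reproduced.

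**Step 2: k subjects unsettled, count of exactly 2.** Only m = 12 − k subjects could have registered a response. Assume all eventual responders among those m are already counted. The limit is the 0.90 quantile of Beta(3, m − 2).

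| k | m | P(X ≤ 2) at 39% | Confidence | 90% upper limit for 2/m |
|---|---|---|---|---|
| 0 | 12 | 0.0946 | 90.5% | 38.6% |
| 1 | 11 | 0.1328 | 86.7% | 41.5% |
| 2 | 10 | 0.1840 | 81.6% | 45.0% |
| 3 | 9 | 0.2511 | 74.9% | 49.0% |

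One unsettled subject is enough to fall below 90%.

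**Step 3: smaller counts.** For a count of 1, P(X ≤ 1) at 39% is 0.023, 0.035, 0.053 and 0.079 for k = 0 to 3, with upper limits of 28.8%, 31.0%, 33.7% and 36.8%. Confidence against 39% stays at 92% or more, and a count of 0 is stronger still. With k up to 3, only the count of exactly 2 is affected.

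**Step 4: plausible k.** With even accrual of a subjects per month, k is about (63 / 30.44) × a + 1. This gives 2.0 at a = 0.5 and 3.1 at a = 1; both rates are assumed. If entries are evenly spaced, one every 9 weeks leaves 1 subject with a single scan, one every 4 weeks leaves 3, and one every 2 weeks leaves 5 (P(X ≤ 2) = 0.44). These are upper values, because each such subject who has already progressed or discontinued is settled and moves the limit back one row. The limits are too low if late responders among the m are still uncounted.

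**Step 5: if a first-scan partial remission counts.** All 12 can then register a response, and the calculation in Step 1 applies to response as scored at the cut-off. It does not carry over fully to the eventual ORR. If half of the eventual responders among the k show a partial remission at the first scan (assumed), confidence for the eventual ORR is 88.6%, 86.4% and 83.8% for k = 1, 2 and 3.

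**The case for a change.** The best case for a change is that the margin is thin and wording is cheap. The plan's 90.5% has almost no slack. Under the Section 2.1 timing, k = 1 needs no accrual assumption: it arises whenever the last subject is still on treatment without progression. Section 7.1.2.7.2 itself warns that responses to immunotherapy can come late. A non-binding rule still feeds a quoted confidence level into a decision, so the level should be right. Faster accrual would make the shortfall much larger, as Step 4 shows.

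It stands that, at a count of 2, the 39%/90% statement does not carry over to the eventual 12.7-defined ORR unless all 12 are settled, and that Section 8.7 is silent on unconfirmed responses. Three things weaken the case for acting on it.

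- The plan can be read as scoring response at each assessment. Section 2.1 ties the look to the first assessment, and Section 7.1.2.8.1 has response determined alongside the scan schedule. On that reading the bound is valid for what is observed.
- The larger shortfalls depend on assumed accrual, and the cohort closed for lack of it. From the original protocol (11 December 2015) to closure (30 April 2019) is about 40 months. Even the full target of about 30 would average 30 / 40 = 0.75 per month. This is only an indication, because the start of Signal Detection is not given.
- Each possible change gains little. Stating that unconfirmed responses count records a convention without restoring 90% for the eventual ORR. Waiting for a second assessment costs about 9 weeks and gives up the early look, and no CLL look remains to be delayed. Withdrawing the 90% figure leaves no single replacement, since the right value depends on k.

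**Conclusion.** The observation is right in a narrow form, and no change to the plan follows. At exactly 2 of 12, one unsettled subject gives about 87% confidence instead of 90%, and an upper limit of about 41.5% instead of 38.6%. Two or three would give 82% or 75%, but those values of k rest on assumed accrual. Counts of 0 or 1 are unaffected for k up to 3, and settled non-responders do no harm.

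Looking after the first scan is a fair trade-off between speed and maturity for a rule that only prompts a review of all the data. Section 8.3 tests no hypothesis. In an open-label trial the team would see any subject whose partial remission was pending and weigh it in that review. The silence on unconfirmed responses is a gap that analysts fill sensibly: if a CLL look took place, which the documents do not say, the study report would describe how response was scored and how many of the 12 were unsettled. Section 1.0 records the CLL cohort as closed with all subjects off treatment, so no future decision depends on the wording. The final CLL ORR and its exact interval under Section 8.6.1 do not use the interim statement.
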